Statistical Analysis Plan

Study Title: Improving Treatment Outcomes for Prescription Opioid Dependence

NCT Number: NCT02543944

Date last reviewed by IRB: 10/4/2021

Data Analysis Methods:

We will compare baseline characteristics of the two groups using the intent-to-treat sample with analyses of variance for continuous variables (e.g., age) and Chi² analyses for categorical variables (e.g., sex, race) to determine whether any significant baseline differences have accrued despite randomization. In addition, given that later phases (i.e., transition, depot NTX therapy) may have different sample configurations due to anticipated dropout, we will similarly compare the two groups on participant characteristics. If we find significant baseline differences in variables within a phase or at each subsequent phase relative to the one prior, these differences will be informative of factors associated with treatment outcomes. For those variables found to affect outcome, we will use contingency tables with stratification or add these factors to the appropriate random regression models to adjust for these differences.

Our primary outcome is changes in opioid positive urines over time during the detox phase. Other major outcomes are: percentage of detox phase completers, naltrexone phase initiators and vivitrol receivers.

Specific Aim 1: Efficacy and tolerability of GBP versus Placebo during and immediately following BUP detox.

For data during the BUP taper (weeks 2-3), dependent variables obtained at several time points (e.g., urine sample results for opioids, opioid withdrawal symptoms scores) will be entered into random regression models, also known as hierarchical linear models (HLMs), to determine whether scores change differentially across treatment groups [154, 155]. Continuous data will be analyzed longitudinally with MIXREG, an HLM modeling program for continuous measures [156]. Dichotomous urine results (i.e., negative or positive) will be analyzed longitudinally using the SAS procedure GLIMMIX, which allows an HLM modeling program for ordinal outcome measures [157]. We will use all available data in our analyses and will make no attempt to interpolate missing data. HLM methodologies fit a regression line for each participant, effectively interpolating missing data, before deriving final estimates. This approach of modeling repeated measures is specifically designed for use in repeated measures designs with missing data, allowing for intra-participant serial correlation and unequal variance and covariance structures over time. These problems, common to clinical trial data, are solved by incorporating available trend data for each individual with information on the behavior of the group from which the participant is drawn. If there are any significant baseline differences, the variable will be added as a cofactor in the HLM analyses. We will examine differences in retention using Kaplan-Meier Survival Analysis. Analyses will be done on those who participated long enough to start the BUP taper, as well as during GBP induction to detect possible differential dropout before the taper. To determine whether treatment group differences occurred in 1) success of retention from the BUP detox to the NTX transition and 2) eligibility to undergo oral NTX induction, we will build 2 X 2 contingency tables using percentages of participants in the GBP vs. placebo groups who 1) return on day 1 of week 4 versus drop out after completing the taper, and 2) test negative versus positive for opioids. The type, severity, and frequency of adverse events will be compared across groups. All analyses will employ a significance level of $\alpha = 0.05$, and all tests are two-tailed.

Specific Aim 2: Acceptability and feasibility of outpatient transition to and maintenance on depot NTX therapy. Because there are two phases to NTX therapy transition (i.e., 4-day oral induction and up to 8-week depot NTX), data obtained during these phases will be analyzed separately. For the oral NTX induction, descriptive statistics will be used to report the percentage of abstinent participants who receive the 4-day oral dosing. Urine data collected each day during the 4-day induction will be entered into random regression models similar to those above to determine whether changes in illicit opioid or other drug use occurred over time. To obtain pilot data on the association between treatment group (GBP vs. placebo) and successful induction, data regarding the percentage of those receiving oral NTX and the NTX injection or not in the GBP vs. placebo groups will be entered into a 2 X 2 contingency table. The type, severity, and frequency of opioid withdrawal and/or adverse events will be compared across groups. Reasons for not receiving the NTX injection will be summarized.

For the NTX phase (weeks 4-12), dependent variables obtained at weekly time points (e.g., urine sample results for opioids and other drugs, side effect scores, opioid withdrawal scores, etc.) will be entered into random regression models (HLMs) to determine whether scores change differentially over time [154, 155]. Continuous data will be analyzed longitudinally with MIXREG [156]. Dichotomous urine results (i.e., negative or positive) will be analyzed longitudinally using the SAS procedure GLIMMIX [157]. We will examine differences in study dropout during this phase using Kaplan-Meier Survival Analysis. Our principal analyses will be done on those who participated long enough to start the depot NTX therapy. The type, severity, and frequency of adverse events will be recorded and summarized.

Specific Aim 3: Identify prognosticators of treatment outcomes. Predictors of treatment efficacy during each phase will be examined using baseline assessments (e.g., sex, level of opioid use, distress tolerance

scores, etc.). We will evaluate general predictors of successful outcomes (with success as defined above) regardless of treatment type and predictors of differential response to treatments. Depending on the distribution of participants with moderate versus severe opioid dependence, severity of opioid dependence will also be examined as a prognosticator. Our basic analytic strategy will be to dichotomize groups into the presence and absence of a dichotomous predictor variable (e.g., female or alcohol dependence diagnosis) and then to examine the relative predictive values on treatment outcomes by adding each factor to the log linear analyses for single time point outcomes and HLM for longitudinal measures such as frequency of self-reported drug use, opioid-negative urines and craving measures. Each continuous measure (e.g., HAM-A, distress tolerance scores) will be entered as a covariate in the above analyses.

Longer-Term Outcomes. Continuous data from the 16-week follow-up interview will be initially entered into repeated measures ANOVA's with group (GBP vs. placebo), successful completion of detox (yes vs. no), successful induction onto oral NTX therapy (yes vs. no), and successful transition to depot NTX therapy (yes vs. no) as factors. Dichotomous follow-up data will be entered into Chi² tables for each phase. Longitudinal data captured during each phase of the study and at follow-up will be entered into random regression models as above, and piece-wise comparisons will be made between each phase. For all analyses, a p value <0.05 will be used to infer statistical significance.

Sample Size. PASS (Power Analysis & Sample Size) Software was used to estimate power. Sample size for the intent-to-treat sample was determined based on having enough power during and immediately following the BUP taper to detect group differences in the primary outcome of illicit drug use and identify potential prognosticators. Based on the proportion of participants in the GBP versus placebo groups having opioid-free urines on the last day of the BUP taper from our pilot trial with GBP [31, 129], treating the one missing value as positive, a difference in the percentage of participants with opioid-free urines at the end of detox as well as immediately prior to initiating NTX therapy will be detected with >90% power with an analysis sample size of 106 total participants anticipated to remain for NTX transition. Thus, our sample size is adequate to detect differences for our primary outcome during and immediately following the detoxification. Meanwhile, there has been minimal, if any, study of sex (or other bivariate prognosticator) differences for the effect of an adjunct medication for opioid dependence, much less for prescription opioid dependence. This study will provide unique data to quantify a potential difference. Given our expected sample size of 150 participants entering the BUP detox phase, the study will have >80% power for an effect size of 0.29 (small effect size), and 106 participants eligible for NTX transition will have >80% power to detect an effect size of 0.35 (considered a "medium" effect size).

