We will compare baseline characteristics of the two groups using the intent-to-treat sample with analyses of variance for continuous variables (e.g., age) and Chi² analyses for categorical variables (e.g., sex, race) to determine whether any significant baseline differences have accrued despite randomization. In addition, given that later phases (i.e., transition, depot NTX therapy) may have different sample configurations due to anticipated dropout, we will similarly compare the two groups on participant characteristics. If we find significant baseline differences in variables within a phase or at each subsequent phase relative to the one prior, these differences will be informative of factors associated with treatment outcomes. For those variables found to affect outcome, we will use contingency tables with stratification or add these factors to the appropriate random regression models to adjust for these differences.

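### Between-arm baseline differences within a phase are read as pointing to outcome-related factors, and significant ones enter the HLMs as cofactors, although the comparison tests arm balance only

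*SAP*

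**What the plan says.** The SAP's opening paragraph under Data Analysis Methods, repeated in Protocol section 8, tests the two arms against each other on baseline characteristics with ANOVA or chi-square. The stated purpose is "to determine whether any significant baseline differences have accrued despite randomization". Because dropout may change who is present in later phases, the plan adds that "we will similarly compare the two groups on participant characteristics" there too.

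The interpretation follows: "If we find significant baseline differences in variables within a phase or at each subsequent phase relative to the one prior", then "these differences will be informative of factors associated with treatment outcomes". No test and no comparison groups are named for the words "at each subsequent phase relative to the one prior".

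Two adjustment rules come next, and they differ:

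- Opening paragraph: "For those variables found to affect outcome, we will use contingency tables with stratification or add these factors" to the regression models.
- Specific Aim 1: "If there are any significant baseline differences, the variable will be added as a cofactor in the HLM analyses". These HLMs include the GLIMMIX model for urine results during the taper, and the SAP names change in opioid-positive urines over the detox phase as the primary outcome.

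Specific Aim 3 separately relates baseline factors to outcomes in each phase, both regardless of arm and as modifiers of the treatment effect. Protocol section 3 lists taper completion and depot NTX induction among its targets.

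**The concern.** The null hypothesis of the specified test is that the arms are balanced on a variable. The conclusion drawn is that the variable is related to outcome. These are different hypotheses. A strong predictor of dropout can be perfectly balanced between arms, and an irrelevant variable can be imbalanced by chance.

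Two things are at stake. First, the report could name factors as outcome-related on the strength of an arm imbalance, alongside and possibly in conflict with the Aim 3 results. Second, the Aim 1 rule lets the same kind of test decide what enters the primary model, so the covariates would follow chance imbalance instead of prognostic strength and would not be known until the data are seen.

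**Working it through.** The plan gives no figure for this inference, so there is none to reproduce.

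**Inputs from the documents.** 150 participants enter detox and 106 remain for NTX transition (SAP, Sample Size): retention 106/150 = 70.7%, with 44 lost. Tests are two-sided, and "For all analyses, a p value <0.05 will be used to infer statistical significance".

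**Assumptions.** 75 per arm (no allocation ratio is stated); one binary baseline factor X with 50% prevalence; odds ratios (OR) for staying chosen for illustration, because the documents give none.

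**Step 1. Why the arm comparison cannot see a shared predictor.** Let r1 and r0 be the probabilities of staying with and without X. At 50% prevalence the share with X among stayers is r1/(r1 + r0). If r1 and r0 are the same in both arms, so is this share, and the expected arm difference is zero however strong X is.

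At OR 3 with 70.7% retained overall, r1 ≈ 0.82 and r0 ≈ 0.60:

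- share with X among stayers, either arm: 0.82/1.42 = 0.577
- share with X among leavers: 0.18/0.58 = 0.310
- stayers minus leavers: 0.267
- SE under the null, pooled share 0.5: √[0.25 × (1/106 + 1/44)] = 0.0897
- SE under the alternative: √[0.577 × 0.423/106 + 0.310 × 0.690/44] = 0.0847
- power ≈ Φ[(0.267 − 1.96 × 0.0897)/0.0847] ≈ Φ(1.08) = 0.86

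**Step 2. Simulation, 20,000 trials per setting, X acting equally in both arms.**

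| OR of X for staying | GBP v placebo among stayers | Stayers v leavers |
|---|---|---|
| 1 | 5.1% | 5.0% |
| 2 | 5.0% | 48% |
| 3 | 5.3% | 85% |
| 4 | 4.8% | 96% |
| 6 | 5.2% | 99.8% |

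The 85% agrees with Step 1. A separate simulation with a standard normal X (4,000 trials per setting) behaves the same way. At log odds ratios of 0.4, 0.5, 0.7 and 1.0 per SD, the arm comparison rejects in 4.3%, 4.9%, 5.5% and 5.7% of trials, and stayers v leavers in 58.3%, 76.3%, 95.8% and 99.9%.

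**Step 3. When arm also affects staying, or changes the effect of X.** Rejection rates for GBP v placebo among stayers:

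- X OR 3 and arm OR 3: 9%
- X without effect on placebo, OR 6 on GBP: 15%
- X OR 0.4 on placebo, 2.5 on GBP: 27%
- arm OR 3, X without effect: 5.2%

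In the third setting the pooled stayers-v-leavers test rejects only 7% of the time, because the opposite effects cancel. A factor-by-arm term is therefore needed as well.

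**Step 4. Chance flags.** With k independent null variables, P(at least one flag) = 1 − 0.95^k: 40% for k = 10 and 64% for k = 20. The number of variables is assumed. Balancing by the urn (Protocol section 7.E) lowers this for the variables it uses.

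**Step 5. The two adjustment rules.** The opening paragraph makes adjustment conditional on a variable being found to affect outcome, but does not say how that is established. The Aim 1 rule drops the condition: significance of the baseline difference is enough. A variable that is imbalanced but unrelated to outcome is included under Aim 1 and excluded under the opening paragraph. A strong predictor that is balanced is not included under Aim 1.

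**The case against.** **Aim 3 already finds predictors.** This stands. It relates baseline factors to outcome directly, whatever the arm, and covers taper completion and NTX induction. A reader might infer that the trial will overlook what predicts reaching NTX transition. The documents do not support that.

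**The opening paragraph restricts adjustment to variables that affect outcome.** On its face this is so, and that paragraph alone does not drive adjustment by imbalance. The unrestricted rule is the one under Aim 1.

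**The 5% is built in.** It follows from giving X the same effect in both arms. After dropout, an arm difference among stayers can signal differential attrition, which is a sound reason to look. A systematic difference there does require X to be related to staying in at least one arm. But in the settings of Step 3 such a factor is flagged 9% to 27% of the time, against 5% for a null variable. One flag is therefore weak evidence about staying, and says less about urine results or other outcomes.

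**The phase-to-phase wording may mean something better.** It may. A reader might take it as an independent-groups test of each phase's sample against the larger sample that contains it, and charge the plan with that test's loss of power. The plan names no such test. The fair criticism is that the comparison is unspecified.

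**To call a difference informative is not a decision rule.** That is fair for the opening paragraph. The Aim 1 sentence is a decision rule.

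**Conclusion.** The point holds in a limited form. A GBP-v-placebo baseline difference within a phase describes balance and, after dropout, possible differential attrition. It is not evidence that a variable affects outcome, and for a factor acting equally in both arms the test performs no better than chance. That last statement does not depend on the size of the factor's effect. The stayers-v-leavers figures do, so the gaps in power (for the normal X, 54 points at log odds ratio 0.4 and 94 points at 1.0) are illustrative.

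The harm is twofold: an invalid second route to naming outcome-related factors beside Aim 3, and covariate selection by baseline significance in the Aim 1 HLMs, the primary urine model included. A reader might go further and infer that the primary treatment comparison is biased. Nothing in the documents or in this check shows that. What is shown is that its covariates are left to be decided by the data, on a criterion unrelated to prognosis.

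**What to change.** 1. In the opening paragraph of the SAP's Data Analysis Methods and of Protocol section 8, replace the interpretive sentence with: *Between-arm comparisons of baseline variables within a phase are descriptive. They show balance and possible differential attrition, and will not be taken as evidence that a variable affects outcome.*
2. Define the phase-to-phase comparison: *At each transition (taper start, taper completion, oral NTX start, depot NTX), participants who continue will be compared with those who do not, by logistic regression on the baseline factor, arm and their product. These analyses belong to Aim 3 and are exploratory.*
3. Replace the significance-triggered cofactor rule under Specific Aim 1 with a covariate list fixed in advance on prognostic grounds, for example the variables already used in the urn and its strata (withdrawal severity, marijuana and tobacco use, anxiety, sex, prescribed psychoactive medication). Make the opening paragraph refer to the same list, so that one rule applies throughout.

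The cost is a few sentences in both documents and some additional models on data already collected. The models will be imprecise, since only about 44 of 150 participants are expected to be lost before NTX transition. They partly overlap with Aim 3 and carry no multiplicity control, so they should be labelled accordingly.

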
3. Purpose:

The specific aims are the following:

Specific Aim 1. Determine the tolerability and efficacy of GBP (1600 mg/day) to reduce withdrawal symptoms, craving, and illicit use of opioids in prescription opioid -dependent individuals undergoing BUP detox. Our hypothesis is that GBP will be well tolerated and reduce, relative to placebo, illicit use of opioids during and immediately following the BUP detox. Gabapentin may also reduce secondary outcomes of withdrawal symptoms and craving relative to placebo during and/or immediately following the BUP detox.

Specific Aim 2. Determine the acceptability and feasibility of transitioning patients completing detox to depot NTX. Our hypothesis is that the majority of those abstinent immediately post-detox will be successfully transitioned to depot NTX.

Specific Aim 3. Determine prognosticators of completion of the BUP taper, successful induction onto depot NTX, symptomatology, and longer-term outcomes at the 16-week follow-up. Mediators (e.g., changes in ratings over time) associated with outcomes will also be explored.

4. Background:

Opioid dependence continues to be a serious public health problem, particularly with the dramatic rise in abuse of prescription opioids [1]. Prescription pain relievers were second to marijuana in terms of prevalence of dependence or abuse in 2009 [1]. Moreover, the number of emergency department visits in 2009 involving narcotic pain relievers was 137% higher than the 2004 level of 144,644 visits [2]. Prescription-opioid abuse is associated with serious negative consequences that include physiological dependence, high-risk behaviors [3, 4], overdose [5, 6], and death [7-9]. Particularly concerning, the rate of current nonmedical use of prescription opioids increased 17% from 2002 to 2009 among young adults aged 18–25 [1]. This project seeks to address the problem of opioid dependence by improving upon detoxification strategies for opioid dependence.

The three existing FDA-approved treatments for opioid dependence were developed in trials with heroin users and include agonist maintenance with methadone or buprenorphine (BUP), methadone- or BUP-assisted detox, and maintenance on the opioid antagonist naltrexone (NTX) in post-opioid dependent patients. Each of the three approaches has significant drawbacks for prescription opioid abusers.

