B. Experimental Procedures. During the detox phase (weeks 1-3), participants will attend the Center for Addiction Services and Treatment on the 4th floor of PRI 3-6 days per week to receive study medication, attend a weekly therapy session, and complete assessments (**Table 1**). During the NTX induction (week 4), participants will attend clinic 4-5 days. On day 1 (either Monday or Tuesday) of week 4, participants will submit a urine sample that may need to be opioid-negative in order to start NTX induction. (If the urine sample is positive for opioids then the decision to start NTX induction will be made by a study physician). Upon daily confirmation of an opioid-negative urine sample or determination by study physician to proceed with NTX induction, participants will be administered clonidine, followed by oral NTX (6.25 mg). Participant's orthostatic vital signs and symptoms will be monitored prior to and 20 minutes following clonidine administration as well as 2 hours after initial oral naltrexone administration. If the participant experiences lightheadedness or dizziness and has evidence of orthostatic hypotension with BP drop of > 20 mm Hg for systolic or >10 mm Hg for diastolic, accompanied by an increase in pulse of more than 20 beats per minute, then the vitals will be repeated in 30 minutes. If the orthostatic changes persist at the time of the second measurement prior to naltrexone administration, then naltrexone will not be administered and vitals will be repeated every 30 min until they are within study parameters for release.

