During the detox phase, morning GBP/placebo ingestion will occur under supervision 6 days per week, and a take-home dose will be given each day for evening ingestion (3 take-home doses on Sat to also cover Sun). For participants on the truncated schedule due to COVID-19 (thrice weekly), lockboxes with BUP and GBP/Placebo will be given on the same schedule to be taken on days when not presenting to clinic (Tues, Thurs, weekends) with specific instructions provided by CAST nurse, in addition to drug accountability logs signed by the participant. Additional take-home doses of GBP/placebo will be given to take on holidays, days when clinic is closed due to inclement weather and holidays to ensure adequate blood levels of GBP are maintained. The initial dose of GBP at 100 mg will be given on day 3 of week 1, and a 100 mg dose provided to take home. The GBP dose will increase to 200 mg BID on day 4, 400 mg BID on day 5, 600 mg BID on day 6, and 800 mg BID (1,600 mg/day) on day 7 of week 1. Participants will remain on 1600 mg/day through day 2 of week 5 (during NTX therapy, GBP/placebo capsules will be given in weekly blister packs). Then GBP will be reduced to 1200 mg/day on day 3, 800 mg/day on day 4, 600 mg on day 5, 400 mg on day 6, and 200 mg on day 7. On days 1 and 2 of week 6, all participants will receive placebo. If GBP side effects are too severe at the 800-mg BID dose, GBP will be decreased to no less than 1200 mg/day, given data that 900 mg/day of GBP is ineffective [97]. If GBP side effects are too severe at 1200 mg/day, GBP will be discontinued and the participant will be discharged from the study and referred to local treatment agencies. During transition to NTX (week 4), if a) the participant's urine sample is opioid-negative and/or regular opioid use is not indicated, *and* b) orthostatic vital signs and symptoms are within limits specified below (Section 14, Protection of Participants, B. Protections Against Risk): On day 1 of week 4, participants will receive 0.1 mg of clonidine followed 20-30 min later by 6.25 mg of oral NTX. If tolerated, the person will return on day 2, receive 0.1 mg of clonidine followed 20-30 min later by 6.25 mg of oral NTX. On day 3, participants will receive 12.5 mg of NTX 20-30 min after clonidine. (For those who do not start induction until day 2 or 3: Starting on day 2, NTX will be given at the 6.25 mg dose 20-30 min after clonidine. On day 3, NTX will be given at the 12.5 mg dose 20-30 min after clonidine.) On day 4, 25 mg of NTX will be given 20-30 min after clonidine. If 25 mg is tolerated, then on the morning of day 5, participants will receive the depot NTX injection. (Participants have up to day 3 of week 4 to start the transition to NTX. For those who do not start induction until day 2 or 3: Starting on day 2, NTX will be given at the 6.25 mg dose 20-30 min after clonidine. Starting on day 3, NTX will be given at the 12.5 mg dose 20-30 min after clonidine. In such cases, dosing/administration on subsequent days will be as specified above.) Those

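### The primary analysis reads as a group-by-time test on weeks 2-3 urines, which has only its alpha against a GBP benefit already present at week 2 and held constant

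*SAP*

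**What the plan says.** The SAP (Data Analysis Methods) states: "Our primary outcome is changes in opioid positive urines over time during the detox phase". Its Specific Aim 1 section, repeated in Protocol section 8, sets the data window: "For data during the BUP taper (weeks 2-3), dependent variables obtained at several time points". These variables "will be entered into random regression models, also known as hierarchical linear models (HLMs), to determine whether scores change differentially across treatment groups". Dichotomous urine results go to GLIMMIX. No fixed effects are listed, and no contrast is named as the primary test.

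Other places describe something else:

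- **Hypothesis** (Protocol section 3, Aim 1): GBP will "reduce, relative to placebo, illicit use of opioids during and immediately following the BUP detox".
- **Test of Aim 1** (Protocol 7.I, after Table 1): drug-screen results are compared between groups in weeks 2-3 and on day 1 of week 4.
- **2 x 2 table** (SAP Aim 1): opioid-negative versus positive by group, offered as eligibility for oral naltrexone.
- **Power** (SAP Sample Size): percentage opioid-free at the end of detox and just before naltrexone.
- **Detox phase** (Protocol 7.B): "During the detox phase (weeks 1-3), participants will attend", so the phase named in the primary outcome is a week longer than the model window.

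On the GBP schedule, Protocol 7.C says "The initial dose of GBP at 100 mg will be given on day 3 of week 1", with the target of "800 mg BID (1,600 mg/day) on day 7 of week 1" and no reduction until week 5.

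**The concern.** A question about differential change is answered by the group-by-time term. The hypothesis is about level. The two coincide if the arms start the window equal and then separate. In weeks 2-3 that start is not assured, because GBP has been taken since day 3 of week 1 and is at target before the first week 2 urine. The window contains no pre-GBP sample. Any benefit that exists when it opens falls in the group term, which the plan does not name as the primary test.

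If the analyst follows the stated purpose, a trial in which GBP lowers opioid-positive urines steadily through the taper could be reported as negative on its primary outcome. A benefit that narrows would give a slope difference pointing against GBP.

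**Working it through.** **Inputs from the documents.** Urines are typically taken three times weekly (Protocol 7.I), so about 6 in weeks 2-3 and 9 in weeks 1-3. The buprenorphine (BUP) taper starts on day 3 of week 2 and ends on day 5 of week 3 (7.C). Tests are two-sided at 0.05. 150 participants enter detox and 106 are expected to remain, a loss of 44/150 = 29.3%. The allocation ratio is not stated; 1:1 is assumed (75 per arm, 53 retained).

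**The plan's own figure.** The power of more than 90% with 106 can be neither confirmed nor refuted, because the pilot proportions are not given. What it requires can be solved from

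n per arm = [1.960·√(2p̄(1−p̄)) + 1.282·√(p₁(1−p₁)+p₂(1−p₂))]² / (p₂−p₁)².

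For 20% versus 49.5% opioid-free, p̄ = 0.3475 and n = (1.320 + 0.821)² / 0.295² = 4.58/0.0870, about 53. Likewise 30% versus 61%, 40% versus 71% and 50% versus 80%. So 90% power needs a gap of about 26 to 31 points for placebo rates of 10-50%. This is a level difference at one time point. It says nothing about power for a slope difference.

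**What each contrast tests.** Scale time t from 0 (start of window) to 1 (end of taper) and write

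logit P(positive) = β₀ + β₁·group + β₂·t + β₃·group·t + participant effect.

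| Shape of benefit δ | β₁ | β₃ (group-by-time) | β₁+β₃ (end of taper) |
|---|---|---|---|
| Constant | δ | 0 | δ |
| Growing from zero | 0 | δ | δ |
| Shrinking to zero | δ | −δ | 0 |

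Under a constant benefit the group-by-time null is true, so that test rejects at its alpha whatever the sample size. The end-of-taper contrast equals δ under both the constant and the growing shape.

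**Simulation, assumed inputs.** Random-intercept logistic data, SD 1 or 2; 75 per arm with dropout to 106 of 150; placebo about 50% positive at the start, rising by 1.0 in log-odds; GBP effect −1.0 to −1.5. Analysis used logistic regression with participant-clustered standard errors, a stand-in for GLIMMIX. For orientation, in the constant case −1.0 with SD 2 gives 64.8% versus 49.9% positive at the last visit, and −1.5 with SD 1 gives 69.6% versus 39.8%. Rejection rates, as ranges over SD and effect:

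| Shape | Group-by-time | Average group contrast | Joint 2-df | 2 x 2 at last visit |
|---|---|---|---|---|
| Constant (4,000 runs) | 5.0-5.4% | 71-100% | 62-100% | 35-88% |
| Growing from zero (800 runs) | 40-88% | 23-91% | 39-98% | 36-90% |
| Shrinking to zero | 37-84%, against GBP | 23-87% | 49-99% | 4-5% |
| Weeks 1-3 window, onset in week 1 (2,000 runs) | 57-97% | 47-100% | 66-100% | 34-87% |

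The last-visit column is nearly the same for constant and growing benefits, as the algebra predicts.

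**Other assumed inputs.** With SD 1.5-2.5, placebo rising from 40% to 60% and GBP on average 25 points lower, group-by-time had 5-6% at both N=106 and N=150; the joint test had 91-98% and 98-99.9%. With a benefit growing to 30 points (N=106), group-by-time had 88-95%. A further set of runs gave, under a constant benefit, 5-6% for group-by-time, 85-100% for the joint test and 78-100% for the end-of-taper contrast from the model. Group-by-time had 68-92% under a growing benefit.

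**The case against.** A reader might infer that the primary test can see no GBP benefit at all. The documents do not support that, for four reasons.

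- **Model terms.** None are listed, so a group effect is neither specified nor excluded. The phrase about differential change describes a purpose, not a contrast.
- **Level comparisons exist.** Protocol 7.I, the 2 x 2 table and the power statement all compare levels.
- **Window.** If the detox phase is weeks 1-3, onset falls inside it and group-by-time largely detects it.
- **Expected shape.** Both arms take 12 mg BUP on the first two days of week 2, a dose that Protocol 7.C associates with minimal withdrawal symptoms. GBP is put forward as a treatment for withdrawal. A benefit that emerges as BUP falls is a reasonable expectation, and group-by-time is a sensible contrast for it.

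All four stand as limits on the claim. They do not remove it. No level comparison is named as the primary test, and the SAP's Aim 1 model is confined to weeks 2-3. Protocol section 13 (Gabapentin) also reports that the same dose reduced craving and opioid use in patients stabilized on BUP, so a benefit present before the taper is plausible too. The documents establish neither shape.

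A joint 2-df test is a tempting cure, but it has no direction. In one set of runs it rejected 71-98% of the time when the arms had converged by the end of the taper, where an end-of-taper estimate would be near zero.

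**Conclusion.** The concern holds in limited form. As worded, the primary outcome and the model's only stated purpose point to a group-by-time test. That test has about 5% power against a benefit that is present at the start of week 2 and constant on the logit scale. This result is algebraic and does not depend on the simulated rates. It conflicts with the level hypothesis, with the group comparison in Protocol 7.I and with the quantity that was powered.

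It would go too far to say that the test is blind to GBP, or that the trial will be reported as negative. That needs the slope reading, the weeks 2-3 window and a constant benefit together. All the other power figures rest on assumed rates, variances, dropout and 1:1 allocation, and they move widely with those assumptions. The point should be settled before the urine data are analysed by arm, because the primary conclusion can turn on it.

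**What to change.** In SAP Specific Aim 1:

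1. State one window for the primary analysis and reconcile it with the detox phase of Protocol 7.B.
2. List the GLIMMIX fixed effects: group, time and group-by-time.
3. Make the primary test the model-estimated GBP-placebo difference in opioid-positive urines at the end of the taper (β₁+β₃ above), and report it also as a difference in probability.
4. Report group-by-time, and the joint 2-df test if wanted, as secondary.
5. Restate the primary outcome sentence and the power statement in terms of this contrast, giving the pilot proportions used.

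The end-of-taper contrast matches the quantity in the Sample Size section and responds to both constant and growing benefits. Data and model stay the same. The costs are SAP wording, a recheck of the power statement, some power lost against an average contrast if the benefit is in fact constant, and none at all against a benefit that has gone by the end of the taper.
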